4.3 Sample Size

This study is designed to show a difference between risankizumab and placebo in terms of achieving 90% reduction in Psoriasis Area and Severity Index (PASI 90) response and sPGA of clear or almost clear (sPGA of 0 or 1) at Week 16. This study was also powered to show a difference in sPGA response at Week 52 between the subjects re-randomized to continue on risankizumab vs. subjects randomized to placebo at Week 28.

Based on the interim results from Study 1311.2, it is assumed at most 10% of the subjects in the re-randomized risankizumab arm and approximately 25% of subjects in the re-randomized placebo arm will lose response. Using a 1:2 re-randomization scheme (risankizumab:placebo), 102 subjects in the risankizumab arm and 204 subjects in the

placebo arm will provide at least 90% power to detect the difference in sPGA response rate at Week 52. Assuming that 80% of subjects initially randomized to risankizumab at baseline will achieve sPGA of 0 or 1 at Week 28, the total sample size required for the initial risankizumab arm at Visit 2 is $(102)(3) \div 0.8 = 383$.

A total sample size of 500 = 400:100 for risankizumab: placebo was planned at Visit 2.

Based on the outcome from Trials 1311.1 and 1311.2, the PASI 90 response rate at Week 16 is assumed to be at least 65% in the risankizumab arm and approximately 5% for placebo. For sPGA clear or almost clear at Week 16, the response rate is assumed to be at least 80% for the risankizumab arm and approximately 5% for placebo. This trial will have > 99% power for comparing risankizumab arm to placebo on both of these endpoints.

All calculations were performed using ADDPLAN Version 6.0.4, an Aptiv Solutions Company.

4.4 Interim Analysis

Unblinded data will be reviewed during the study by an independent data monitoring committee (DMC). The membership, roles and responsibilities and activities of the DMC will be defined in a written charter. The DMC will include representatives from external safety experts who do not directly involve in the study. Clinical site personnel and the study team will remain blinded to the randomized treatment assignments during the course of the study. Communications from the DMC to the study team will not contain information that could potentially unblind the study personnel. Since there is no efficacy analyses for early stopping, no alpha adjustment is needed.

5.0 Analysis Populations

5.1 Definition for Analysis Populations

Efficacy Population:

Intent-to-Treat (ITT) Population: The ITT Populations will be used for the efficacy analyses in different parts.

- The ITT Population in Part A1 (ITT_A1) is defined as all subjects who are randomized at Baseline. This Population will be analyzed for the efficacy of initial treatment.
- The ITT Population in Part A2 from Arm 1 (ITT_A2) is defined as all subjects who were randomized to Arm 1 at Baseline. Data from Part A2 will be used to evaluate the mid-term efficacy.
- The ITT Population across Part A2 and B from Arm 2 (ITT_ARM2) is defined as all subjects who were randomized to Arm 2 at Baseline and received at least one dose of study drug on or after Week 16. This Population will be analyzed for short and long term efficacy without initial loading dose.
- The ITT Population in Part B for re-randomized subjects (ITT_B_R) is defined as all subjects who were randomized to Arm 1 and re-randomized at Week 28. The ITT_B_R Population will mainly be used to compare efficacy of continued treatment with risankizumab vs withdrawal from the treatment. The risankizumab arm will also be summarized (including data after retreatment) for long-term efficacy with the option of re-load.
- The ITT Population in Part B for Arm 1 non-responders at Week 28 (ITT_B_NR) is defined as all subjects who were randomized to Arm 1 at Baseline, were non-responders (sPGA ≥ 2) at Week 28, and receive at least one dose of risankizumab on or after Week 28. This population will be summarized for potential delayed response.
- The ITT Population for Part B placebo patients who received retreatment (ITT_B_PBO_RT) is defined as all subjects who were re-randomized to placebo and received at least one dose of retreatment with open label risankizumab after relapse, and have the opportunity to have retreatment Week 16 assessments.

- The ITT Population for Part B risankizumab patients who receive retreatment (ITT_B_RZB_RT) is defined as all subjects who were re-randomized to risankizumab and received at least one dose of retreatment with open label risankizumab after relapse, and have the opportunity to have retreatment Week 16 assessment. The population will be summarized to examine the efficacy of re-treatment with loading dose upon relapse on risankizumab.

ITT Populations will be analyzed by the treatment group as randomized.

In addition, additional analysis will be performed on ITT_B_R subjects who are re-randomized to risankizumab 150 mg, in which all evaluations after re-randomization (including evaluations after retreatment with open label risankizumab after relapse) will be included along with the blinded assessments to evaluate the efficacy of continuous treatment.

Per-Protocol (PP) Population: To evaluate the impact of protocol deviations on the primary and ranked secondary endpoints, additional analyses will be performed on the Per-protocol Populations. The Per-protocol Population will include those who were most compliant with the protocol in ways that could impact the primary and ranked secondary endpoints. Final results and the criteria for exclusion of subjects will be finalized prior to database lock for data pertaining to the DB period.

The PP Population at Part A1 (PP_A1; a.k.a. the PPS in study Protocol 1311.4) is defined as all subjects from the ITT_A1 Population who meet all the following criteria:

- Subjects must receive at least 75% of planned study drug injections, per randomization, in Part A1.
- Subjects must have either a PASI or sPGA assessment post-baseline in Part A1.
- Inclusion Criterion 4: Subjects must have stable moderate to severe chronic plaque psoriasis at baseline:
 - Have an BSA $\geq 10\%$ and
 - Have a PASI ≥ 12 and

- Have an sPGA ≥ 3 .

Primary and ranked secondary efficacy endpoints at Part A1 at Week 16 will be analyzed on the PP_A1 Population.

The PP Population at Part B for re-randomized subjects (PP_B_R; a.k.a. RRS-PPS in study Protocol 1311.4) is defined as all subjects from the ITT_B_R Population who meet all the following criteria:

- Subjects must receive at least 75% of planned study drug injections, per re-randomization, in Part B.
- Subjects must have at least one sPGA assessment post re-randomization in Part B.
- Subjects must have sPGA < 2 at re-randomization.

The primary efficacy endpoint for Part B at Week 52 and ranked secondary endpoint for Part B at Week 104 will be analyzed on the PP_B_R Population.

PP Populations will be analyzed by the treatment group as randomized (or re-randomized).

Safety Population:

The Safety Populations will be used for safety analyses in different study parts.

Each ITT population will have a corresponding safety population (Safety) of the same study part, which includes all subjects who receive at least one dose of study drug during the analysis period.

Complete safety tables will be provided for the Safety_A1 Population and the Safety_B_R population. Only AE overview tables will be provided for other safety populations.

The Safety Population will be analyzed based on the actual treatment received at the randomization visit (Part A) and at the re-randomization visit (Part B).

In addition, an All Risankizumab Treated Population (ALL_RZB) is defined as all subjects who receive at least one dose of risankizumab in the study. The ALL_RZB Population will be used for safety analyses. Complete safety tables will be provided in the ALL_RZB Population.

Table 1. Notations for Treatment Groups

Population	Treatment Code	Definition
ITT_A1/PP_A1/ Safety_A1	RZB	Subjects who randomized to risankizumab 150 mg.
	PBO	Subjects who randomized to placebo.
ITT_A2/Safety_A2	RZB/RZB	Subjects who randomized to risankizumab 150 mg.
ITT_ARM2/ Safety_ARM2	PBO/RZB	Subjects who randomized to placebo and received at least one dose of study drug on or after Week 16.
ITT_B_R/PP_B_R/ Safety_B_R	RZB/RZB/RZB	Subjects who re-randomized to risankizumab 150 mg at Week 28.
	RZB/RZB/PBO	Subjects who re-randomized to placebo at Week 28.
ITT_B_NR/Safety_B_NR	RZB/RZB/RZB	Subjects who randomized to risankizumab and are non-responders at Week 28.
ITT_B_PBO_RT/ Safety_B_PBO_RT	RZB/RZB/PBO/RZB	Subjects who received open-label risankizumab 150 mg as retreatment, after re-randomized to placebo in Part B.
ITT_B_RZB_RT/ Safety_B_RZB_RT	RZB/RZB/RZB/RZB	Subjects who received open-label risankizumab 150 mg as retreatment, after re-randomized to risankizumab in Part B.
ALL_RZB	RZB	Subjects who received at least one dose of risankizumab 150 mg.

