3.3.3. Exclusion criteria

1. Patients with
 - nonplaque forms of psoriasis (including guttate, erythrodermic, or pustular)
 - current drug-induced psoriasis (including a new onset of psoriasis or an exacerbation of psoriasis from beta blockers, calcium channel blockers, or lithium)
 - active ongoing inflammatory diseases other than psoriasis and psoriatic arthritis that might confound trial evaluations according to the investigator's judgment

2. Previous exposure to BI 655066
3. Currently enrolled in another investigational study or less than 30 days (from screening) since completing another investigational study (participation in observational studies is permitted).
4. Use of any restricted medication as noted in [Table 4.2.2.1:1](#) or any drug considered likely to interfere with the safe conduct of the study.
5. Major surgery performed within 12 weeks prior to randomisation or planned within 12 months after screening (e.g. hip replacement, removal aneurysm, stomach ligation,).
6. Known chronic or relevant acute infections, such as HIV (Human Immunodeficiency Virus), viral hepatitis, or tuberculosis. QuantiFERON® TB test or Purified Protein Derivative (PPD) skin test will be performed during screening. Patients with a positive test result may participate in the study if further work up (according to local practice/guidelines) establishes conclusively that the patient has no evidence of active tuberculosis. If presence of latent tuberculosis is established, patients who are at low risk of reactivation, defined by local guidelines and investigator judgment, do not need to be treated with prophylactic anti-tuberculosis prior to or during the trial.
7. Any documented active or suspected malignancy or history of malignancy within 5 years prior to screening, except appropriately treated basal cell carcinoma or squamous cell carcinoma of the skin or in situ carcinoma of uterine cervix.
8. Evidence of a current or previous disease (including chronic alcohol or drug abuse), medical condition other than psoriasis, surgical procedure (i.e., organ transplant), medical examination finding (including vital signs and ECG), or laboratory value at the screening visit outside the reference range that in the opinion of the Investigator, is clinically significant and would make the study participant unable to adhere to the protocol or to complete the trial, compromise the safety of the patient, or compromise the quality of the data.

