4.2.2 Restrictions

4.2.2.1 Restrictions regarding concomitant treatment

The medications (or classes of medications) listed in [Table 4.2.2.1:1](#) must not be taken for the specified times prior to randomisation and for the whole duration of the study. If prohibited medication is used during the study for any indication, the patient must discontinue use of the prohibited medication if he/she wants to continue in this study. If a patient receives a live virus during the study, they must be discontinued.

Proprietary confidential information © 2016 Boehringer Ingelheim International GmbH or one or more of its affiliated companies
Table 4.2.2.1:1 Restricted medications

Medication or class of medications	Restriction duration (through EOO Visit)
guselkumab, tildrakizumab	not allowed prior or during trial participation
briakinumab, secukinumab (Cosentyx®), ustekinumab (Stelara®)	6 months prior to randomisation
brodalumab, ixekizumab	4 months prior to randomisation
adalimumab (Humira®), infliximab (Remicade®)	12 weeks prior to randomisation
investigational products for psoriasis (non biologics)	
etanercept (Enbrel®)	6 weeks prior to randomisation
live virus vaccinations	6 weeks prior to randomisation
investigational device or product (excludes psoriasis products)	
other systemic immunomodulating treatments (e.g. methotrexate, cyclosporine A, corticosteroids ¹ , cyclophosphamide, tofacitinib (Xeljanz®), apremilast (Otezla®))	30 days prior to randomisation
other systemic psoriasis treatments (e.g. retinoids, fumarates, any other drug known to possibly benefit psoriasis)	
photochemotherapy (e.g., PUVA)	
phototherapy (e.g., UVA, UVB)	14 days prior to randomisation
topical treatment for psoriasis or any other skin condition (e.g. corticosteroids ² , vitamin D analogues, vitamin A analogues, pimecrolimus, retinoids, salicylvaseline, salicylic acid, lactic acid, tacrolimus, tar, urea, andanthralin, α-hydroxy, fruit acids)	

¹ No restriction on corticosteroids with only a topical effect (e.g. inhalant corticosteroids to treat asthma or corticosteroid drops used in the eye or ear).

² **Exception:** Topical steroids of US class 6 (mild, such as Desonide) or US class 7 (least potent, such as hydrocortisone) will be permitted for use limited to the face, axilla, and/or genitalia with a restriction of use within 24 hours prior to clinic visits when PASI is assessed.

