7.3 PLANNED ANALYSES

The efficacy analyses will be based on the intent-to-treat principle, comprising all participants who were randomized and received at least one dose during the trial. Misrandomized patients are by definition screening failures and therefore are not included in the intended to treat population. Efficacy analyses will be based on the planned treatment (i.e., the treatment assigned at randomisation); this set of patients is called the Full Analysis Set (FAS). Safety analyses will be based on the actual treatment received at the randomisation visit; this set of patients is called the Safety Set (SAF).

All efficacy analyses will be conducted on the FAS. All safety analyses will be conducted on the SAF.

Important violations of the protocol will include key inclusion and exclusion violations, incorrect medications taken, compliance with study medication, incorrectly re-randomized or not re-randomized, concomitant use of restricted medications, and any other violations of the protocol deemed important by the study team. All decisions concerning important protocol violations will be made prior to unblinding of the database. A per-protocol set (PPS) will be defined excluding patients with violations that affect Week 16 efficacy. A secondary re-randomized per-protocol set (RRS-PPS) will be defined excluding those patients with violations affecting Week 52 efficacy of randomized withdrawal. The hypothesis tests as described in Section 7.2 will be repeated on the PPS or RRS-PPS populations, as appropriate.

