7.4 Protocol Deviations

Number and percentage of subjects who reported at least one of the following protocol deviation categories will be provided.

- Subject entered into the study even though she/he did not satisfy entry criteria
- Subject who developed withdrawal criteria during the study and was not withdrawn
- Subject who received wrong treatment or incorrect dose
- Subject who received excluded or prohibited concomitant treatment

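### SAP 5.1 narrows the Protocol 7.3 per-protocol sets without saying so: washout breaches and restricted psoriasis medication do not remove a patient, and PP_B_R does not check baseline severity

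*SAP*

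**What the plan says.** Protocol 7.3 first says what counts as an important violation: "Important violations of the protocol will include key inclusion and exclusion violations, incorrect medications taken, compliance with study medication", then errors in re-randomisation, then "concomitant use of restricted medications, and any other violations of the protocol deemed important by the study team". It builds the two sets from that. For Part A: "A per-protocol set (PPS) will be defined excluding patients with violations that affect Week 16 efficacy". For Part B, the re-randomised set (RRS-PPS) "will be defined excluding those patients with violations affecting Week 52 efficacy of randomized withdrawal". Decisions on important violations must be made before unblinding, and the Section 7.2 tests are repeated on these sets.

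Restricted medication is both an entry rule and an on-study rule. Exclusion 4 in Protocol 3.3.3 bars "Use of any restricted medication as noted in" Table 4.2.2.1:1, and Section 4.2.2.1 says the listed drugs "must not be taken for the specified times prior to randomisation and for the whole duration of the study".

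SAP 5.1 states that PP_A1 is the protocol's PPS and PP_B_R its RRS-PPS, and gives each a list of criteria that must all be met:

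- PP_A1 (drawn from ITT_A1): at least 75% of planned injections, a post-baseline PASI or sPGA, and "Inclusion Criterion 4: Subjects must have stable moderate to severe chronic plaque psoriasis at baseline", followed by the BSA, PASI and sPGA thresholds.
- PP_B_R (drawn from ITT_B_R): at least 75% of planned injections in Part B, one sPGA after re-randomisation, and sPGA below 2 at re-randomisation.

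SAP 7.4 tabulates deviations by category, one of which is "Subject entered into the study even though she/he did not satisfy entry criteria" and another prohibited concomitant treatment. It does not link them to the per-protocol sets. SAP 14.1 records only that the analysis populations, including per-protocol, were defined in detail.

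**The concern.** SAP 5.1 gives the purpose of these sets as measuring how protocol deviations affect the primary and ranked secondary endpoints. Recent prior therapy, and psoriasis treatment taken on study, are among the deviations most able to move PASI 90 and sPGA, yet neither list tests for them. If the per-protocol result agrees with the intent-to-treat result, readers will take that as robustness to deviations that were never removed.

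SAP 14.1 presents the definition as added detail, so a reader comparing the two documents is not told that the rule has changed. The protocol text was not incidental. Its amendment log says the wording on important violations and the per-protocol analyses was added to Section 7.3 after health authority questions, in place of a deferral to the SAP.

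**Working it through.** **1. Planning figures used below.** The point rests on no figure in the plan, but the illustration in step 5 uses the planned arm sizes. For 90% vs 75% at 1:2, two-sided 0.05 and 90% power, with pooled rate (0.90 + 2×0.75)/3 = 0.80:

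n = [1.960×√(0.80×0.20×1.5) + 1.282×√(0.90×0.10 + 0.75×0.25/2)]² / 0.15² ≈ (0.960 + 0.549)² / 0.0225 ≈ 101.3, so 102 active and 204 placebo. Power at 102:204 is 90.2%, and 102×3/0.8 = 382.5, so 383. This reproduces Protocol 7.7.

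**2. The protocol's violation classes against the SAP lists.**

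| Protocol 7.3 class | PP_A1 | PP_B_R |
|---|---|---|
| Key inclusion violations | Inclusion 4, at baseline | Not tested |
| Key exclusion violations | None named; the plaque wording in Inclusion 4 partly covers Exclusion 1 | None named |
| Incorrect medication, compliance | At least 75% of injections as randomised: 3 of 4 | At least 75%: 9 of 12 if not retreated |
| Wrongly re-randomised | Not applicable | Partly: sPGA below 2 |
| Restricted concomitant medication | Not tested | Not tested |

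Of 6 inclusion and 11 exclusion criteria, PP_A1 names one and PP_B_R none. PP_B_R is drawn from ITT_B_R and not from PP_A1, so it does not inherit Inclusion 4.

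**3. Three patients followed through the rules.**

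- A listed biologic was taken inside its washout; dosing, assessments and baseline severity are in order. Protocol 7.3: a breach of Exclusion 4 that can plausibly affect Week 16, so out. SAP: in PP_A1.
- Restricted psoriasis medication was taken before Week 16, or between re-randomisation and Week 52; dosing and assessments are in order. Protocol 7.3: a listed violation, out if it affects efficacy. SAP: in.
- A patient was randomised to active drug in error with PASI 6 and sPGA 2, reached sPGA 0 at Week 28 and was re-randomised. SAP: out of PP_A1, in PP_B_R.

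**4. Does another rule catch them?** Protocol 7.5 counts visits after prohibited psoriasis medication as failures for binary endpoints. The matching note in SAP 10.1.4 names only discontinuation for worsening disease and retreatment, so that rule is not carried over. Protocol 7.3 keeps misrandomised patients out of the intent-to-treat set, but SAP ITT_A1 takes everyone randomised. The SAP cites the protocol of 28 July 2016. The log for the October 2016 revision lists only 7.3.4 among Section 7 changes, so the version gap does not explain the difference.

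**5. Illustrative size (counts assumed).** If k violators in an arm of n all respond and the others respond at the planned rate p, the arm reads p + k(1−p)/n. Removing them returns it to p.

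- Part A placebo (p = 5%, n = 100): k = 1, 2, 4 give 5.95%, 6.9%, 8.8%. With k = 2, the 4:1 ratio suggests 8 in the active arm: 65% + 8×0.35/400 = 65.7%. The PASI 90 difference is then 58.8 points instead of 60.
- Part B placebo (p = 75%, n = 204): k = 2, 4, 8 give 75.2%, 75.5%, 76.0%. With k = 4, the 1:2 ratio suggests 2 in the active arm: 90% + 2×0.10/102 = 90.2%. The difference is then 14.7 points instead of 15.

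**The case against.** **The criteria were still open.** SAP 5.1 says the exclusion criteria will be finalised before database lock, and the protocol leaves important violations to the study team. This softens the point. But the lists are worded as complete definitions, and the sentence names no entry or medication rule still to be added.

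**The protocol does not require every breach to be excluded.** This stands. Key is not defined, and only violations that affect efficacy count. A reader might infer that all 17 entry criteria should be tested; the protocol does not support that. Nothing in the documents suggests that diagnosis duration (Inclusion 3) or a repeat severity check at Screening would move Week 16 response, since response is measured from baseline.

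**Part B is weaker.** This also stands. A reader might infer that PP_B_R has no eligibility check; it does test the re-randomisation criterion. A washout breach before baseline lies about a year before Week 52, so it is not the argument for Part B. What remains there is restricted medication after re-randomisation and the dropped Inclusion 4.

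**Exclusion 1 is not wholly ignored.** Agreed: the plaque wording in Inclusion 4 covers non-plaque disease on its face, though the tests listed under it concern severity only.

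**The effect is small.** Agreed as far as can be told. A reader might take four mild entrants among 204 as a 2-point shift (4/204 = 2.0%). That counts patients, not their effect; at a planned rate of 75% the shift is at most 0.5 points.

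**Conclusion.** The point holds as a conflict of rules, not as missing detail. SAP 5.1 claims to implement the protocol's PPS and RRS-PPS, but its closed lists omit washout breaches and restricted psoriasis medication, and PP_B_R omits Inclusion 4. SAP 14.1 does not disclose the narrowing. The conflict is clearest for Part A washouts and for restricted medication in either part.

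It rests on two readings: that the SAP lists are complete as written, and that a washout breach or on-study psoriasis treatment can affect the skin endpoints.

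The consequence is confined to the per-protocol sensitivity analyses. A reader might infer a threat to the primary result; there is none, because the intent-to-treat analysis, sample size and alpha do not depend on these sets. The documents give no violation rate, so the effect on the per-protocol results cannot be quantified, and the counts in the working only illustrate its scale.

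**What to change.** In SAP 5.1:

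- Add to PP_A1: no violation of Exclusion 4 (the Table 4.2.2.1:1 washouts), Exclusion 1 or Exclusion 2, and no restricted psoriasis medication before the Week 16 assessment.
- Add to PP_B_R: met Inclusion 4 at baseline, and no restricted psoriasis medication between re-randomisation and the Week 52 assessment (Week 104 for the ranked endpoint).

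Take the flags from the underlying deviation data and fix them before unblinding, as Protocol 7.3 already requires. The SAP 7.4 table cannot supply them, because it gives only counts by category with all entry failures pooled. If the narrower sets are intended, state in SAP 14.1 that the Protocol 7.3 rule was narrowed, and why.

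The cost is SAP wording and a few programming flags, with a separate medication cut-off for Week 104. The per-protocol sets become slightly smaller. Removing patients for medication taken after randomisation can also remove treatment failures unevenly, so the number excluded should be reported by arm and reason.
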